Walking on tile and carpet at participant's natural speed ^e		X																	
Capture time-activity blocks; moving naturally between activities' stations ^g		X																	
Device exposure – (APDM collection)		X																	
Device exposure – (In-Lab ActiGraph collection)		X																	
Wearability/Comfor t questionnaire		X															X		

090177e19d2ca190\Approved\Approved On: 12-Apr-2023 20:13 (GMT)

Procedure/ Assessment	In-Lab		At-home monitoring															Final study evaluation	Return of Study Materials
	Screening	Visit 1	Day 1	Day 2	Day 3	Day 4	Day 5	Day 6	Day 7	Day 8	Day 9	Day 10	Day 11	Day 12	Day 13	Day 14	Day 15	Day 15 (+3 days)	
	Day 1	Day 1																	
Cognitive debrief of wearability/comfort questionnaire		X																	
Participant chooses paper or electronic activity diary		X																	
Instruct participant and parent/LAR on use of ActiGraph		X																	
Device exposure- (At-Home ActiGraph provisioning) ^d			X																
At-home monitoring with ActiGraph devices ^d			X	→	→	→	→	→	→	→	→	→	→	→	→	→	→	X	
Electronic Activity diary ^h				X	X	X	X	X	X	X	X	X	X	X	X	X			
Paper Activity diary ^h				X	X	X	X	X	X	X	X	X	X	X	X	X			
Phone interview ⁱ																		X	
Collect Paper Activity diary																			X
Device exposure – (At-Home ActiGraph collection) ^j																			X
Device assessment ^j		X	→	→	→	→	→	→	→	→	→	→	→	→	→	→	→	X	
Adverse event monitoring ^k	X	→	→	→	→	→	→	→	→	→	→	→	→	→	→	→	→	X	

Procedure/ Assessment	In-Lab		At-home monitoring															Final study evaluation	Return of Study Materials
	Screening	Visit 1	Day 1	Day 2	Day 3	Day 4	Day 5	Day 6	Day 7	Day 8	Day 9	Day 10	Day 11	Day 12	Day 13	Day 14	Day 15	Day 15 (+3 days)	
	Day 1	Day 1																	

- a. Medical/Surgical history, prior/concomitant treatment will be recorded by a medically qualified individual.
- b. Leg length is measured by the clinician utilizing a flexible tape measure with the participant in supine position. The leg length will be measured from the Anterior Superior Iliac Spine to the Medial Malleoli on the right side. The measurements will be recorded in the CRF.¹
- c. APDM Opal sensors placed on left wrist, right wrist, chest, lumbar, left foot, right foot.
- d. ActiGraph placed on non-dominant wrist and lumbar, serial numbers of both devices to be collected on CRF for every participant.
- e. Natural speed is participant's self-chosen pace.

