- b. Leg length is measured by the clinician utilizing a flexible tape measure with the participant in supine position. The leg length will be measured from the Anterior Superior Iliac Spine (ASIS) to the Medial Malleoli (MM) on the right side. The measurements will be recorded in the CRF.¹
- c. APDM Opal sensors placed on left wrist, right wrist, chest, lumbar, above left foot, right foot.
- d. Panoramic Bracelet device placed on non-dominant wrist and lumbar region, serial numbers of device to be collected on CRF for every participant.
- e. Natural speed is participant's self-chosen pace.
- f. Varied speeds include participant's self-chosen slow pace ("Walk slow") and fast pace ("Walk fast").
- g. Participant will alternate between activities' stations. Participants will do ~7 minutes of activities, ~5 minutes of break and ~7 minutes of activities. The task stations include 2 sitting activities, 2 standing activities, and 2 walking activities. Order of stations will be determined at random using dice roll.
- h. Phone call visit to complete Comfort and Wearability Questionnaire for Panoramic Bracelet and advise participant to don the GENEActiv
- i. The participant will be asked to perform an approximately 10 minute walk outside of the lab.
- j. The study staff will instruct the participants to mail back both devices at the final study evaluation over the phone at the exit interview.
- k. Any event with a device (issues with devices, loss of the devices, etc.), the impact of this event and the action taken with device will be recorded in a device assessment CRF.
- l. Adverse events (AEs) will be queried at the clinic visit and during the exit phone interview using open-ended and nonleading verbal questioning of the participant. Any spontaneously reported AEs noted during the home visits will be captured during the exit phone interview.

RATIONALE AND BACKGROUND

This is not a post-authorization safety study (PASS) and is not a commitment or requirement to any regulatory authority.

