parent(s)/LAR. The investigator must ensure that each participant and participant's parent(s)/LAR is fully informed about the nature and objectives of the trial and possible risks associated with participation. If the participant's parent(s)/LAR desires the participant to participate in the study and the participant wishes to participate in the study, an IRB-approved informed consent form will be signed and dated by the participant's parent(s)/LAR and a verbal or written assent from the participant will be collected (if applicable, as consistent with the participant's age and ability to provide assent), as required by the IRB. The informed consent and assent forms must be agreed by Pfizer and the IRB and must be in compliance with the International Council for Harmonisation (ICH) Good Clinical Practice (GCP), local regulatory requirements, and legal requirements.

The signed documents will be retained at the site, and the investigator or person designated by the investigator must document in the source documents that informed consent and assent were obtained.

The participant will be assigned a participant identifier after informed consent and assent are obtained.

Visit 1 (Day 1)

After informed consent and assent have been obtained, the following assessments will be performed during the study visit:

1. Collect participant demography and parent(s)/LAR's contact information.
2. Obtain medical and surgical history.
3. Review prior and concomitant treatments.
4. Confirm eligibility for the study based on inclusion/exclusion criteria.
5. Record height, leg length, and weight.
6. Handedness questionnaire: [Edinburgh Handedness Inventory \(EHI\)-short form \(Annex 4\)](#).
7. Place device under study and APDM devices on participant.
8. Walk on a GAITRite® walkway at participant's natural speed (3 rounds = ~20 feet x 3) and at varied speeds while wearing device under study and APDM system. Natural speed is participant's self-chosen pace and varied speeds includes participant's self-chosen slow pace ("Walk slow") for 3 rounds and fast pace ("Walk fast") for 3 rounds.
9. Walk on tile and carpet (3 rounds on each surface) at participant's natural speed while wearing device under study and APDM system.

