The performance of the following assessments in lab will be recorded in a CRF at Visit 1 (Day 1):

- To walk on a GAITRite® walkway at participant's natural speed.
- To walk on a GAITRite® walkway at varied speed (slow pace).
- To walk on a GAITRite® walkway at varied speed (fast pace).
- To walk on tile.
- To walk on carpet.
- To walk naturally between activities' stations first time.
- To walk naturally between activities' stations second time.
- Free walking condition outside lab for cohort B only.
- Each participant will have up to 3 attempts for each task. If the participant attempts the task, the performance should be recorded under column titled "Successfully perform task?" with options of "Yes", "No", or "Not Done".

Devices Assessment and Exposure

Cohort A: APDM opal devices will be worn during Visit 1 only on both wrists, both feet, lumbar, and waist. Device under study (ActiGraph) will be worn during visit 1 and also during the at-home monitoring portion between Day 1 and Day 15+3 days on the non-dominant wrist and waist.

Cohort B: APDM opal devices will be worn during Visit 1 only on both wrists, both feet, chest, and waist. Device under study (Panoramic Bracelet) will be worn during visit 1[wrist and lumbar] and also during the at-home monitoring portion between Day 1 and Day 15+3 days on the non-dominant wrist. GENEActiv device will be worn on the same non-dominant wrist from Day 7+2 until the end of study [Day 15+2] approximately for 7 days consecutively.

Any event with a device (issues with devices, loss of the devices, etc), the impact of this event and the action taken with device will be recorded anytime between Day 1 and Day 15+3 days in a device assessment CRF.

DATA ANALYSIS/STATISTICAL METHODS

Study Size

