#### 6.3.2. To assess the ability of pediatric participants to perform a battery of lab-based tasks

The total number of participants able to perform each of the 7 tasks (i.e., walking at natural, slow and fast speeds, tile and carpet walks, 2 sessions of in-lab simulated activities) will be summarized overall and by age group. The number of tasks performed by each participant (out of a total of 7 tasks) will be derived and expressed as a percentage. Descriptive statistics of this percentage across participants will be computed.

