### **6.3.6. To evaluate the effect of floor surface (carpet vs. tile) on gait metrics collected using ActiGraph and APDM devices.**

The effect of floor surface will be evaluated on gait metrics extracted from APDM and Actigraph worn on the lumbar position (Section 3.2., Table 4).

The following analyses and plots will be provided (see Table 10):

- Box and whiskers plots of gait parameters by floor type.
- The effect of floor type on gait parameters will be analyzed using paired tests (paired t-test or Wilcoxon Signed-rank test), and the effect size will be computed per device.
- Mixed model regression analyses will be used to investigate the effect of device (APDM vs Actigraph), and device by floor type (carpet vs tile) interaction. The device, floor type, and their interaction will be fixed effects, and subject will be entered as random effect. Post-hoc t-tests might be performed between devices. Multiple comparisons, when necessary, will be performed using FDR. Age (or age group) and sex may be used as covariates in the model. The estimates for fixed effect parameters, standard errors, 95% CIs, and p-values, as well as the variance estimates for the random effect will be summarized. Results from all models will be presented in a table. Furthermore, Least Squares Means (LSMeans) together with their 95% CI will be calculated for each device-floor-type combination.

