### 6.6.2. To evaluate the effect of floor surface (carpet vs tile) on gait metrics collected using Panoramic Bracelet and APDM devices.

The effect of floor surface will be evaluated on gait metrics extracted from APDM and Panoramic Bracelet devices (Section 3.3, Table 7). Same analyses plan will be implemented as listed in Section 6.3.6.

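### The order of the tile and carpet walks is not set, balanced, recorded or modelled, so the floor effect may be confounded with walk order

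*Protocol*

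**What the plan says.** Protocol, Study Procedures, Visit 1 (Day 1), step 9, has each child do both surfaces in the same session: "Walk on tile and carpet (3 rounds on each surface", at natural speed, wearing the study device and the APDM set. Both Schedules of Activities have a single row, "Walking on tile and carpet at participant's natural speed", with no footnote on sequence. Performance of In-lab Tasks has separate entries, with "To walk on tile" directly before the carpet entry, and records only whether each task was performed successfully. SAP 6.3.2 lists "tile and carpet walks, 2 sessions of in-lab simulated activities".

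The effect of floor surface is a secondary objective in Cohort A and an exploratory one in Cohort B. SAP 6.3.6 states: "The effect of floor type on gait parameters will be analyzed using paired tests". It adds a mixed model with device, floor type and their interaction as fixed effects, subject as random effect, and age and sex as optional covariates. For Cohort B, SAP 6.6.2 states: "Same analyses plan will be implemented as listed in Section 6.3.6". SAP 3.5 lists candidate covariates, and walk order is not among them. The protocol's limitations section does not mention it either.

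Order and position are controlled elsewhere. Footnote g of both Schedules of Activities says: "Order of stations will be determined at random using dice roll". The at-home position of the two Cohort B wrist devices is balanced within age group.

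**The concern.** The floor comparison is a within-child contrast of two conditions done one after the other. Self-chosen pace in children aged 3 to 17 may drift between the first and second surface through habituation, boredom or tiredness. Gait speed, cadence, stride length and the stance, swing and support times would move with it. The paired test and the floor term credit all of that change to the floor. A real floor effect could be hidden or a false one created. Because the study device and APDM record the same walks, both would show the same shift, and their agreement would not reveal it.

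**Working it through.** **The plan's own figure.** The documents give no sample size, power or effect size for the floor comparison. The only gait sizing figure is for agreement (Protocol, Study Size): ICC 0.72 against a null of 0.27, one-tailed 0.05, power 0.8, at least 17 participants. It reproduces with the Walter-Eliasziw-Donner formula for two measurements:
- C = (1 + 2×0.27/0.73)/(1 + 2×0.72/0.28) = 1.740/6.143 = 0.283
- n = 1 + 4(1.645 + 0.842)²/(ln 0.283)² = 16.54, rounded up to 17
- 17/0.85 = 20 after 15% attrition, doubled to about 40 and set at 39

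This is context only; nothing below depends on it.

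**Inputs.** About 39 children per cohort and 13 per age group (Study Size). Significance at p < 0.05 (SAP 5.1); two-sided is assumed, because sidedness is not stated. The size of an order effect is not given; 0.1 to 0.5 SD of the within-child difference is assumed.

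**Step 1: what the paired test estimates.** Let F be the true floor effect (carpet minus tile), P the shift from first to second surface, and p the share of children who walk tile first. The expected mean difference is

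F + (2p − 1)P.

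- Tile first for all (p = 1): F + P. The whole order shift is counted as floor.
- Exact balance (p = 0.5): F.
- p unknown: a bias of unknown size and sign.

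**Step 2: could the model separate them?** With one order for all, a design matrix with columns for intercept, floor and order has rank 2 of 3, so floor and order are aliased at any sample size. With a 20/19 split the rank is 3 of 3.

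**Step 3: size if one order is used.** With F = 0 and an order shift of d SD, the paired t statistic is noncentral t with n − 1 degrees of freedom and noncentrality d√n. Two-sided rejection rates at 0.05:

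| Assumed d (SD) | n = 39 | n = 13 (one age group) |
|---|---|---|
| 0 | 5% | 5% |
| 0.1 | 9% | 6% |
| 0.2 | 23% | 10% |
| 0.3 | 45% | 17% |
| 0.5 | 86% | 38% |

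**Step 4: size after balancing.** In 20,000 simulated studies per setting, with a 20/19 split and sequence in the analysis, the mean floor estimate was within 0.002 SD of zero. The rejection rate was 4.97%, 4.85% and 5.03% for d = 0.2, 0.3 and 0.5.

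**The case against.** A reader might infer that tile always precedes carpet and that the floor effect is therefore confounded. The documents do not support that. Tile is named first in the procedural lists only; the objectives and SAP 3.5 name carpet first. A list is also not a prescribed sequence. Varying the order, or alternating rounds between surfaces, would comply with step 9. Alternation alone would shrink a steady drift: with tile in rounds 1, 3, 5 and carpet in 2, 4, 6, the mean positions are 3 and 4, against 2 and 5 for two blocks of three. This objection stands, and it makes full confounding conditional on how the visit is run.

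The evidence for drift is thin. The nine earlier walkway passes (three each at natural, slow and fast pace) total about 9 × 20 = 180 feet and come before both surfaces, so they do not by themselves separate the two. The documents contain no data on drift. That also stands, and it is why the rates above are illustrations.

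The comparison of the study device with APDM on a given surface uses the same walk and is not exposed. Table 1 of the protocol gives that comparison as the purpose of the task. This stands, but the floor effect is also a named objective with its own tests.

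Two further points carry less weight. The covariate lists in SAP 5.1 are open-ended, so an order term is not excluded, but it cannot be fitted without knowing the order. The session is filmed and data segments are identified from annotations, so the order may be recoverable, but neither document plans to do this. FDR control, which SAP 6.3.6 allows, would change the rejection rates but not the bias.

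**Conclusion.** The gap is real but conditional. The order of the two surfaces is not specified, counterbalanced, captured as a data item or modelled. If the tasks are run as listed for every child, the floor main effect and the per-device paired floor tests are fully aliased with walk order, and no planned analysis can separate them. If order varies unrecorded, the bias is partial and unknown.

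The range of about 9% to 86% false-positive floor findings at n = 39 assumes a single order, a two-sided test at 0.05 without multiplicity adjustment, no true floor effect, and order shifts of 0.1 to 0.5 SD that the documents neither give nor rule out. It is not an estimate of what happened in this study.

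Same-surface comparisons between the study device and APDM, and every primary objective, are unaffected. Because the exposed objective is secondary in Cohort A and exploratory in Cohort B, severity is low to moderate.

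**What to change.** **Cohort B, children not yet walked.** Assign tile-first or carpet-first about half and half within each age group (7 and 6 of 13) from a pre-made alternating or blocked list. A simple dice roll does not guarantee balance in groups this small. State whether the three rounds on a surface are walked as one block. Record the order on the task CRF, add order (first or second surface) as a fixed effect to the mixed model used under SAP 6.6.2, and take the floor effect from that model.

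**Cohort A, whose planned data collection ended on 01 April 2022, and any Cohort B child already walked.** Recover the order from the video or sensor time stamps. If it varied, add the order term under SAP 6.3.6 or 6.6.2. If it was the same for all, or cannot be recovered, report floor and order as inseparable and list this as a limitation.

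**Cost.** One line in the visit procedure, one CRF field and one degree of freedom, plus the time to read the order off existing recordings. No extra walks are needed.

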ANNEX 1. LIST OF STAND ALONE DOCUMENTS

None.

ANNEX 2. LIST OF GAIT METRICS ENDPOINTS

APDM

- Cadence (steps/min)
- Double support (sec)
- Gait cycle duration (sec)
- Gait speed (meters/sec)
- Initial double support (sec)
- Single limb support (sec)
- Stance time (sec)
- Step duration (sec)
- Stride length (meters)
- Swing time (sec)
- Terminal double support (sec)
- Steps

GAITRite®

- Single support time (sec)
- Double support time (sec)
- Stance time (sec)
- Step length (meters)
- Step time (sec)
- Step velocity (gait speed) (meters/sec)
- Stride length (meters)
- Stride time (sec)
- Swing time (sec)
- Steps (steps)
- Cadence (steps/min)

GaitPy

- Steps (steps)
- Stride duration (sec)
- Step duration (sec)
- Cadence (meters/min)
- Initial double support (sec)
- Terminal double support (sec)
- Double support (sec)
- Single limb support (sec)
- Stance time (sec)
- Swing time (sec)
- Step length (meters)

- Stride length (meters)
- Gait speed (meters/sec)

SIMI system

- Gait speed (meters/sec)

ANNEX 3. LIST OF PHYSICAL ACTIVITY METRICS ENDPOINTS

ActiGraph

- Sedentary time (min)
- Sedentary percentage (%)
- Light time (min)
- Light percentage (%)
- Life-style time (min)
- Life-style percentage (%)
- Moderate-to-Vigorous Physical Activity (MVPA) time (min)
- MVPA percentage (%)
- Total daily activity counts (on each axis, and vector magnitude of 3 axes)
- Total daily calories (calories)

Pfizer Wear Algorithm (GENEActiv, Panoramic Bracelet)

- Number of available hours (h)
- Number of hours of wear (h)
- Number of wear hours while awake (h)

Pfizer Sleep Algorithm (SleepPy - GENEActiv, Panoramic Bracelet)

- Time in Bed (min)
- Percent time asleep (%)
- Number of wake bouts (no.)

- Sleep onset latency (min)
- Wake after sleep onset (min)

[figure not shown]
Pfizer Scratch Algorithm (ScratchPy - GENEActiv, Panoramic Bracelet)

- Total scratch duration (min.)
- Total scratch episodes (no.)

ANNEX 4. EDINBURGH HANDEDNESS INVENTORY – SHORT FORM

Edinburgh Handedness Inventory - Short Form

COPYRIGHTED MATERIAL

ANNEX 5. WEARABILITY/COMFORT QUESTIONNAIRE

Instructions: *If the child is 3 years old to 11 years old, the parent or caregiver (legal representative) should answer the questions. If the child is 12 years old or older, the child can answer the questions.*

Below the word device refers to [insert name of device].

Please select the option below to show how much you agree or disagree with each of the sentences. Each list of questions is specific to one device and its location, eg, a device on your left wrist. The device you are being asked about is listed above.

Select only ONE response.

	Strongly Disagree	Disagree	Neutral	Agree	Strongly Agree
The device is comfortable to wear					
The device is easy to put on					
The device is easy to take off					
The device is easy to wear					
The device changes the way I move					
The device changes the way I behave					
I am willing to wear the device for 4 to 7 days					
I am willing to wear the device for more than 7 days					
If the device could follow my progress during a treatment, I would wear it					
If the device could follow my progress during a treatment, I would want my doctor to have access to my results					

ANNEX 6. ACTIVITY DIARY

Instructions: Please answer these questions every day. If the child is 3 years old to 11 years old, the parent or legally acceptable representative should answer the questions. If the child is 12 years old or older, the child can answer the questions.

1) Were you sick today, or did anything prevent you from doing your normal physical activities (weather, other)?

Yes No

2) Today, did you do sports or physical activities in which you were very active (playing hard, running, jumping, throwing)?

Yes No

If Yes, what was the total time spent? <30 min 30 min - 1h > 1h

ANNEX 7. COGNITIVE DEBRIEF OF WEARABILITY/COMFORT QUESTIONNAIRE

Instructions: If the child is 3 years old to 11 years old, the parent or caregiver (legal representative) should answer the questions. If the child is 12 years old or older, the child can answer the questions.

1. Approximately how long did it take you to complete the wearability questionnaire? (____ minutes).
2. Did you find any of the questions confusing? Yes or No, if Yes, please explain:
3. Did you find any words confusing? Yes or No, if Yes, please list:
4. Do you have suggestions for rewording any questions to make it more clear to you what is being asked? Yes or No, if Yes, please explain:
5. Do you have any other feedback on the questionnaire for us? Yes or No, if Yes, please explain further:
6. Is there anything else that you think would be important to ask?

[figure not shown]
ANNEX 8. ACTIVITY AND SLEEP DIARY

How would you rate the quality of your sleep, last night?*	 Very Poor  Poor  Acceptable  Good  Very Good Reset
How was your level of physical activity yesterday?*	 Less active than usual  Usual  More active than usual Reset

APPENDIX 1: COHORT LISTING AT HOME MONITORING

COHORT NAME	DEVICE(S) [LOCATION OF DEVICE ON BODY]	DESCRIPTION OF DEVICE(S)	DEVICE(S) SENSORS CONFIGURATION ON BODY	HOME MONITORING	ENDPOINTS
A	Lumbar and non-dominant wrist	ActiGraph CentrePoint Insight Watch ⁰		Yes ~14 days	At-home physical activity related endpoints (wrist) At-home gait and sit-to-stand related endpoints (lumbar)
B	Non-dominant wrist	Panoramic Wearable Bracelet		Yes ~14 days	At-home activity related endpoints

X9001263 LOW-INTERVENTIONAL STUDY PROTOCOL
Final Protocol Amendment 1, 10 April 2023

COHORT NAME	DEVICE(S) [LOCATION OF DEVICE ON BODY]	DESCRIPTION OF DEVICE(S)	DEVICE(S) SENSORS CONFIGURATION ON BODY	HOME MONITORING	ENDPOINTS
B	Non-dominant wrist	GENEActiv Watch		Yes ~ Day 7 to 14	At-home activity related endpoints

Document Approval Record

Document Name:	AMENDMENT_1_X9001263_PROTOCOL_10APR2023
Document Title:	AMENDMENT_1_X9001263_PROTOCOL_10APR2023

Signed By:	Date(GMT)	Signing Capacity
PPD	12-Apr-2023 19:52:17	Final Approval
PPD	12-Apr-2023 20:13:06	Final Approval
